2.5.2. Treatment failure

- Failure due to efficacy:** Patients can be declared a treatment failure due to futility and be declared a treatment failure and enter Phase II **at any time during follow-up** if the following occurs: The treating physician determines that it is futile to continue the current study medication due to persistent, uncontrolled inflammation that appears to be non-responsive to treatment. This option of declaring futility should only be declared if treatment with study medication seems completely unlikely to be able to control inflammation. Since the medications take up to a few months to fully take effect, increase in inflammation early on in the trial is not an indication of treatment failure. Corticosteroids may be increased in the case of increased inflammation.

Efficacy will be judged at the primary endpoint of 6 months. Specifically, at 6 months, if there is a lack of efficacy, patients will be declared a treatment failure and enter Phase II if the following occurs: The patient does not have controlled inflammation (see Table 2) with a prednisone dose of 7.5 mg/day and less than or equal to 2 prednisolone acetate 1% drops per day by 6 months.

- Failure due to intolerance:** Patients who experience severe symptoms thought to be related to the drug should try a dose reduction if they are willing. If this is not successful and the patient is unable to continue their

medication due to symptoms and is also not willing to continue, treatment failure can be declared. Please refer to Table 5 for dose reduction guidelines. Trial of a dose reduction is strongly encouraged, however it **is not required** for a patient to be determined a treatment failure due to intolerability.

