4.6.1. Study Procedures

Every attempt should be made to obtain all study procedures at a non-study visit if treatment failure is being declared. However, if this is not possible the required study procedures include the following:

- Clinical eye exam (if treatment failure is declared)

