2.4 Randomization

2.4.1 Stratification between sites

Patients will be recruited from nine sites: [REDACTED]

[REDACTED] (see Manual of Operations Section 2.2 for details). Patients will be randomized to two treatments (arms): methotrexate (X) or mycophenolate mofetil (Y). The treatment protocols are specified in the FAST Uveitis Trial Manual of Operations.

Within each site, assignments will be conducted using a block randomization scheme with randomly varying block sizes.

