The primary analysis is a logistic regression with treatment arm as a predictor. For the primary analysis, we propose to use study site as a *random effect* (random intercept model). The null hypothesis is that the regression coefficient for treatment arm equals zero, which will be tested using a likelihood ratio test with one degree of freedom. We will also fit the following models: (a) a model including drug, site, and drug \times site interaction, (b) a model including only drug and site, (c) a model including only drug and country, and (d) a model with drug, country, drug-country interaction, and site within country. Countries or sites with fewer than three observations will be pooled together. Provided there is no evidence of treatment \times site interaction or treatment \times country interaction, we will report pooled treatment effects and confidence intervals. In the event evidence suggests a difference between treatment sites, we will report treatment effects by site, and repeat the analysis excluding particular sites. Similarly, evidence of a treatment \times country interaction will lead us to report treatment effects and confidence intervals by country.

Simulations suggest that use of a model containing interaction terms between site or country and treatment for the primary analysis is undesirable. Such a procedure results in modest loss of power unless the treatment effect is of opposite sign in different sites or countries.

The hypothesis test is to be two-sided with alpha of 0.05. We propose to compute the P-value by permutation testing, based on the block randomization scheme.

Prespecified Subgroup Analysis.

The prespecified subgroup analysis will test the hypothesis that there is a treatment effect separately in each anatomic group, using a logistic regression model.

We denote the two anatomic groups by X_i^3 , which equals 0 when the patient is in the intermediate group and 1 when the patient is in the posterior/pan group. In the intermediate subgroup, we plan to determine whether there is evidence of a treatment effect (regardless of the effect in the posterior/pan group). Specifically, we will conduct this analysis in two ways: anatomical site at enrollment (split into three categories: anterior, anterior/intermediate or intermediate only, and posterior/panuveitis), and anatomical location by history (split into two

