17. Additional exploratory modeling will be conducted using clustered multinomial logistic regression using all time points and all observations of anterior chamber cells, vitreous haze, and retinal/choroidal lesions.

3.2.3 Specific Aim 2

Primary Analysis.

The primary analysis will compare the proportion of successes between (a) patients treated with mycophenolate mofetil following failure on methotrexate and (b) patients treated with methotrexate following failure on mycophenolate mofetil.

Specifically, we will conduct a logistic regression in which success or failure will be the outcome, and the predictors (regressors, independent variables) will be treatment group and reason for failure of the first drug (lack of efficacy vs any other reason). Supplementary analyses will include anatomic location (intermediate vs posterior/pan) and country. We will test the hypothesis that the coefficient for treatment group equals zero (i.e., that mycophenolate mofetil rescue after methotrexate failure has the same result as methotrexate rescue after mycophenolate mofetil failure). All alpha levels will be two-sided.

It is important to emphasize that estimation of the success rate of the second drug following the failure of the first is a central goal of the trial, arguably as or more important than the hypothesis test itself. The success rates and confidence intervals will be presented regardless of the results of the hypothesis test.

Secondary Analyses.

The following secondary analyses are planned.

We will also present the estimated success proportion in both treatment groups, together with the 95% confidence intervals. The two groups are the individuals who were undergoing methotrexate rescue therapy after mycophenolate mofetil, and those who were undergoing mycophenolate mofetil rescue therapy after methotrexate. Logistic regression will also be used to adjust for study site.

The second prespecified analysis will compare the rate of success between rescue patients and first-line patients, using logistic regression; we will test the hypothesis that the coefficient for rescue/initial equals zero. A supplemental variation of this analysis will include an additional predictor for whether the patient was on rescue therapy due to lack of efficacy, lack of safety or intolerance, or anatomic location. Two separate analyses are planned, each with an alpha of 0.05.

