Thus, the number of available patients for Specific Aim 2 are highly dependent on the results from Specific Aim 1. Scientifically, the result of rescue therapy is important regardless of the result in Aim 1. More power will be available for the primary comparison in Specific Aim 2 if treatment in Specific Aim 1 yielded relatively high and similar failure rates for both drugs. However, even if success rates are very different in Aim 1, the descriptive analyses will still provide important information to guide decision-making on second-line treatment.

Here, $N_0=108$, and r_1 is assumed to be 0.9 (10% loss to follow-up). For planning Specific Aim 2, we assume a success rate of 60% for patients treated with drug A Specific Aim 1, and a success rate of 40% for those treated with drug B. This is a conservative estimate of the difference expected based on retrospective studies^{12, 18-20} and consistent with the pilot study. Finally, we are assuming an additional 5% loss to follow-up during Specific Aim 2 (in addition to the 10% already lost), so that $r_2=0.95$. The results are summarized in the following table, where the number enrolling does not include loss to follow-up, and the “expected complete” column has taken loss to follow-up into account (n_{jk}).

We anticipate the following:

Initial/Second Treatment	Expected Enrollment SA/2	Expected to Complete SA/2
B/A	58.3	55.4
A/B	38.9	36.9

Thus, we expect a total of $n_1=58$ patients (rounding down) to have failed one first-line therapy to be enrolled in rescue therapy. Similarly, we expect $n_0=38$ patients to be enrolled in the other rescue regimen.

Previous observational studies suggest a 42% success rate of mycophenolate mofetil in methotrexate-failing patients.²⁴ A simple power analysis for comparing these proportions may be found from the formula (see Chao et al, p. 87):¹⁵

$$1 - \beta = \Phi \left(\frac{|p_1 - p_0|}{\sqrt{\frac{p_0(1-p_0)}{n_0} + \frac{p_1(1-p_1)}{n_1}}} - z_{\alpha/2} \right)$$

where p_0 is the probability of success with methotrexate rescue following mycophenolate mofetil failure, p_1 the probability of success with mycophenolate mofetil rescue following methotrexate failure, and Φ is the cumulative distribution function of the standard normal distribution. These assumptions yield a power of 0.87 if the rate of success with methotrexate rescue is 0.15. We have approximately 80% power to detect a difference of 17% if the probability of success with mycophenolate mofetil is 0.42.

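### The Aim 2 rescue comparison is between non-randomised groups, and its model leaves out the inflammation measured when Phase I failure is declared

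*Combined protocol and SAP*

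**What the plan says.** SAP 3.2.3 makes the Aim 2 primary analysis a logistic regression of rescue success on "treatment group and reason for failure of the first drug (lack of efficacy vs any other reason". Other covariates come later in the same section. "Supplementary analyses will include anatomic location (intermediate vs posterior/pan) and country", and under the secondary analyses "Logistic regression will also be used to adjust for study site". Exploratory analyses add age, disease and affected region. SAP 3.7 gives the Aim 2 primary analysis its own alpha of 0.05.

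The Aim 1 primary model (SAP 3.2.2) uses "study site as a *random effect* (random intercept model", in line with the design in SAP 2.4.1: "Within each site, assignments will be conducted using a block randomization scheme with randomly varying block sizes".

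The rescue groups form by failure on the randomised drug (protocol 1.2 and 4.1.2); nobody is re-randomised. For planning (SAP 3.4.2), "we assume a success rate of 60% for patients treated with drug A Specific Aim 1", and 40% for drug B. SAP 3.4.1 identifies the 60% drug as mycophenolate.

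Inflammation is recorded at the switch. The form schedule in protocol 4.2 marks the Clinical Eye Exam Form at treatment failure at any time. Protocol 4.6.1 keeps one procedure as the minimum even at a non-study visit: "Clinical eye exam (if treatment failure is declared".

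**The concern.** If one first drug works better, the patients it fails are on average the harder ones. At 60% and 40% success, one group is the worst-responding 40% of its arm and the other the worst-responding 60%. A comparison of rescue success then mixes the effect of the second drug with how difficult each group was to begin with.

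The reason-for-failure term removes part of this. It separates efficacy failures, who are mostly still inflamed, from patients who stopped for tolerability or safety. Within efficacy failures it does nothing. Protocol 2.5.2 defines that category at 6 months as "The patient does not have controlled inflammation (see Table 2) with a prednisone dose of 7.5 mg/day" (with a limit on topical drops as well), so it covers a quiet eye that needs more steroid and a heavily inflamed eye alike.

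At stake is a between-drug test with its own 5% alpha, and therefore advice on which drug to use second. The bias runs the same way as the SAP's planning alternative (0.42 for mycophenolate rescue against 0.15 for methotrexate rescue). SAP 3.2.3 does not say that the contrast is unprotected by randomisation.

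**Working it through.** **1. The plan's own figures.** From SAP 3.4.2, with 108 per arm, 0.9 retained in Aim 1 and 40% or 60% success:

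- methotrexate failures: 108 × 0.9 × 0.6 = 58.3
- mycophenolate failures: 108 × 0.9 × 0.4 = 38.9

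The SAP's power formula with 58 and 38 patients, 0.42 against 0.15, gives

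Φ(0.27 / √(0.15 × 0.85/38 + 0.42 × 0.58/58) − 1.96) = Φ(0.27/0.0869 − 1.96) = Φ(1.146) = 0.874.

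The stated 0.87 reproduces. It is an unadjusted two-proportion calculation.

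**2. Bias from selection.** The documents do not say how strongly severity predicts rescue success, so I assumed a range. One standard normal severity factor lowers the log-odds of success on either drug by b per SD. The rescue drugs are equally good at any given severity, and methotrexate failures succeed on rescue at 42%.

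The planned reason term matters, so non-efficacy failures are included at the rates in SAP 3.4.2: 13% + 5% = 18% on methotrexate and 4% + 5% = 9% on mycophenolate, assumed unrelated to severity. Efficacy failures are then 60 − 18 = 42% and 40 − 9 = 31% of each arm.

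| b (log-odds per SD) | Severity imbalance, all failures efficacy-driven (SD) | Spurious gap, same set-up, no reason term (points) | Spurious gap among efficacy failures, with the SAP's non-efficacy rates (points) | Rejection at nominal 5%, reason in model |
|---|---|---|---|---|
| 0.5 | 0.09 | 1.1 | 0.9 | 4–5% |
| 1.0 | 0.17 | 3.5 | 3.0 | 5% |
| 1.5 | 0.21 | 6.1 | 5.3 | 6.5–7% |
| 2.0 | 0.24 | 8.5 | 7.4 | 7–10% |

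Mycophenolate failures are the sicker group in every row, so the gap favours mycophenolate rescue. The last column comes from simulated trials of 58 and 38 patients and shows the spread over repeated runs; 1,500 trials have a standard error of about 0.6 points near 5%. With severity in the model as well, rejection is about 4% to 6% throughout. A slope of 2.0 is an odds ratio of about 7 per SD (e² = 7.4), which is an extreme assumption.

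**3. Power.** Simulated at 0.42 against 0.15 with a between-site SD of 0.5, comparing no adjustment with adjustment for inflammation and site (reason term left out for simplicity):

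| Imbalance (SD) | b = 0.5 | b = 1.0 |
|---|---|---|
| 0 | 0.845 → 0.862 | 0.831 → 0.893 |
| 0.165 | 0.872 → 0.859 | 0.887 → 0.876 |
| 0.5 | 0.914 → 0.816 | 0.957 → 0.839 |

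Adjustment gains about 2 to 6 points when the groups are balanced. It costs power when mycophenolate failures are sicker, because the unadjusted difference is then inflated. Site alone adds 1 to 3 points (0.849 to 0.863 at a site SD of 0.5; 0.827 to 0.859 at 1.0).

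**4. Room for covariates.** Expected successes are 0.42 × 58 = 24.4 and 0.15 × 38 = 5.7, about 30 in all and about 6 in methotrexate rescue.

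**The case against.** The strongest reply is about what Aim 2 is for. SAP 3.4.2 describes its primary analysis as estimating each rescue success rate with a confidence interval and treats the comparison as one analysis among others. SAP 3.2.3 ranks estimation at least level with the test. Those rates describe what happens to patients who failed a given drug and need no severity adjustment. This stands. The point touches only the between-group test, but that test is named in SAP 3.2.3 and given its own alpha.

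Second, much is already planned: reason for failure in the model, site in a secondary analysis, anatomic location and country as supplementary. Vitreous haze with its baseline value is also modelled among the secondary outcomes repeated for Aim 2, but there haze is the outcome. None of these puts inflammation at the switch into the success model.

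Third, the score is imperfect. It is affected by the first drug and by the steroid dose at the time, and it would rate a quiet eye on too much prednisone as mild. It can also be ungradeable behind a media opacity. All of this stands: the score reduces confounding without removing it. With about six successes expected in one group, a lean model is also a reasonable preference.

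A reader might go further and infer that the planned model loses power, or that omitting site confounds the comparison. The documents support neither. The stated 0.87 is itself unadjusted and reproduces, and adjustment can lower power. Assignment was blocked within site, so site could confound only through differential failure or entry to Phase II. Its absence is mainly an inconsistency with Aim 1.

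**Conclusion.** The gap is real and modest. The Aim 2 test compares groups selected by failing different drugs and leaves out a starting value that the protocol already collects. On the SAP's 60% and 40% rates the residual bias favours mycophenolate rescue by about 1 to 3 points among efficacy failures at slopes of 0.5 to 1.0, and about 7 points at 2.0, against a planned difference of 0.42 − 0.15 = 27 points. The test stays near its nominal 5% at the lower slopes and reaches 7% to 10% only at the extreme one.

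These sizes rest on assumptions: a single severity factor, non-efficacy failure unrelated to it, and non-efficacy failures entering Phase II in proportion, although some safety failures are barred from switching. If the Phase I rates were equal, this route to bias would largely close; if they reversed, so would its direction.

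A reader might infer that the Aim 2 test is seriously invalid. Unadjusted rejection of 9% to 16% does appear if the groups differ by 0.5 SD (slopes 0.5 and 1.0, no reason term), but the SAP's rates imply only 0.09 to 0.24 SD, and nothing in the documents points to more.

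**What to change.** In SAP 3.2.3:

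- Add to the Aim 2 comparison model one ordinal, worst-eye inflammation score from the examination at which Phase I failure is declared (the Phase II starting value), and a random intercept for site as in Aim 1. Define the score before the data are unmasked, including how anterior chamber cells, vitreous haze and active retinal or choroidal disease combine, and how ungradeable fields are handled.
- Report the current two-predictor model alongside it.
- Leave the per-group success rates and confidence intervals as planned.
- State that the contrast is not protected by randomisation and that adjustment cannot restore that protection.

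The cost is wording only, with no new data. There are three downsides. With about 30 successes, the added adjustment must stay at one score plus the site intercept. The odds ratio becomes conditional on the score and site. Power may fall slightly if the groups are imbalanced, by about one point at 0.165 SD.

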3.3 Transformations and model adequacy

3.3.1 Primary Analysis

Sensitivity analyses based on modeling the individuals lost to follow-up will be conducted, however; we will determine how much of a treatment effect there would have had to have been in the patients lost to follow-up, for the results of the main hypothesis test to change.

3.3.2 Unspecified secondary analyses

Unprespecified analyses may be conducted following the primary analysis and will always be reported as such. Analyses will always be repeated including age and gender, in particular.

3.3.3 Model validation and sensitivity

In all cases, standard statistical procedures will always be followed to ensure that no evidence indicates a violation of the assumptions underlying the statistical models used. Specifically, we note the following: secondary analyses based on the use of age as a continuous predictor in logistic regression models with treatment success as an outcome will be assessed using the Hosmer-Lemeshow goodness-of-fit test. Linear models will always be assessed using residual plots (residuals vs. predicted values, and QQ plots), together with tests for normality (Anderson-Darling and Shapiro-Wilk procedures). For mixed models, we will examine marginal residuals, conditional residuals, and EBLUPs.⁸ When modeling binary outcomes (using clustered logistic regressions), we will repeat analyses using a probit link as a check on robustness; we will also examine the Pearson goodness of fit statistic.⁹ Jackknife influence estimates will be used in all analyses; single observations that could change the conclusions will always be reported. Analyses in which time to response is used as the outcome variable (in which Cox regression is conducted) will be supplemented with the Gill-Schumacher procedure for assessing the adequacy of the proportional hazards assumption for Cox regression.¹⁰ Analyses in which our primary interest is in final outcomes will still be repeated using all available data (at all time points).

Failure of the modeling assumptions (such as normality) will result in conducting additional analyses. First, for continuous outcome variables, we will undertake normalizing or variance-stabilizing transformations of the outcome variable (such as power transformations). Second, robust procedures will be used to estimate the standard errors whenever possible. Third, the use of bootstrap procedures, when applicable, will be considered in estimation of standard errors.¹¹

3.4 Sample Size Evaluation

3.4.1 Primary Calculation

The sample size for the trial will be 216 subjects, which we anticipate will provide approximately 80% power to detect a difference of 20% in the proportion of patients achieving control of inflammation at six months between the methotrexate and mycophenolate mofetil groups.

This sample size was determined based on the primary objective (superiority comparison of mycophenolate mofetil to methotrexate) and primary endpoint (treatment success). We assumed an effect size of 20%, as this was deemed to be clinically meaningful, and well within the distribution of the investigators' prior beliefs from published retrospective studies.

An approximate sample size is provided by the formula

$$2N = \frac{4(Z_{\alpha} + Z_{\beta})^2 \bar{p}(1-\bar{p})}{(p_c - p_i)^2} \quad (5)$$

(see Friedman et al. 2010), where α is the significance level (0.05, two sided), β is one minus the power (the desired power is 80%), p_c is in this case the probability of success in the methotrexate group (we estimate this at 0.4), p_i is the probability of success in the mycophenolate mofetil group (we estimate this at 0.6), and \bar{p} is $\frac{1}{2}(p_i+p_c)$. We assume 10% will be lost to follow-up in the first six months; details are given in the full proposal. This yields approximately 108 patients in each of the two groups, for a total of $2 \times 108 = 216$ subjects.

A power table is provided below as a sensitivity analysis (to show how the detectable effect size changes with varying success rates).

Success rate with Drug A	80% Power		90% Power	
	Detectable effect size	Success rate with Drug B	Detectable effect size	Success rate with Drug B
20%	18%	38%	21%	41%
30%	20%	50%	23%	53%
40%	20%	60%	23%	63%
50%	20%	70%	22%	72%
60%	19%	79%	21%	81%

Simulation confirms that this method yields adequate sample sizes for the logistic regression (results not shown).

Note that for the final analysis, the critical value will be adjusted slightly because of the interim analysis.

Sample size readjustment

Simulation suggests that a baseline covariate which is associated with the outcome variable could modestly reduce the sample size needed for 80% power (simulation results are available upon request). Sample size readjustment based on baseline predictors will be considered, subject to approval by the DSMB. The guiding principle is (CHMP, Reflection Paper on methodological issues in confirmatory clinical trials planned with an adaptive design, 2007): Analysis methods that control the type I error must be pre-specified. Whenever possible, methods for blinded sample size reassessment that properly control the type I error should be used, especially if the sole aim of the interim analysis is the re-calculation of sample size.

